9.4 Observation Period for Adverse Events

The observation period for the reporting of AEs (and SAEs) for an individual subject will start at the time of giving written informed consent for participation in the current study and finish 4 weeks after the last visit.

If the investigator becomes aware of an SAE or that has started after the observation period has finished, and there is at least a possible causal relationship to IgPro20 or IgPro10, the event must be reported to CSLB (see [Section 9.6.2](#)).

Medical device incidents or malfunctions that result in an AE are to be reported during all periods of the study in which the medical device is used. If the investigator becomes aware of any incident that has started after a subject has been discharged from the study, and such incident is considered at least possibly related to a medical device provided for the study, the event must be reported to CSLB (see [Section 9.6.3](#)).

9.5 Follow-up of Adverse Events

Every effort should be made to follow AEs until resolution or stabilization. Ongoing, non-serious AEs that have not resolved or stabilized will be followed until the subject completes the study. Serious adverse events will be followed until the AE resolves, stabilizes, or the subject is lost to follow-up or death.

All medical device incidents involving an AE will be followed and reported in the same manner as other AEs.

9.6 Adverse Event Reporting

9.6.1 Adverse Events

At each clinical evaluation, the investigator (or delegate) will determine whether any AEs have occurred. AEs will be recorded in the AE page of the eCRF. If known, the medical diagnosis of an AE should be recorded in preference to the listing of individual signs and symptoms. The investigator must follow-up on the course of an AE until resolution or stabilization. If an AE is ongoing after the EOS Visit, the AE will continue to be followed up until resolution, stabilization, or the subject is lost to follow-up.

If, during the study period, a subject presents with a pre-existing condition that was not noted at the time of study entry, the condition should be retrospectively recorded in the Medical History eCRF.

9.6.2 Serious Adverse Events

This study will comply with all applicable regulatory requirements and adhere to the full requirements of ICH Topic E2A (Clinical Safety Data Management: Definitions and Standards for Expedited Reporting).

For SAEs occurring during the study, the investigator or delegate will enter all relevant information in the eCRF.

All SAEs that occur during the course of the study, whether or not causally related to IgPro20 or IgPro10, must be reported and entered into the eCRF immediately (within 24 hours of the event) to CSLB.

Adverse events occurring in the period between the times the subject gave written informed consent and the first exposure to IgPro20 or IgPro10 that meet 1 or more of the seriousness criteria will be entered into the eCRF in the same manner as other SAEs and will be included in the clinical study database.

Any SAE that occurs after the EOS Visit that is considered to be causally related to IgPro20 or IgPro10 must be **reported immediately (ie, within 24 hours of the investigator becoming aware of the event) to CSLB.**

The minimum reporting requirements for reporting of SAEs include:

- Subject identification number.
- Suspected medicinal product and / or procedure.
- Event term.
- Reporting source identification.

If the minimum requirements for reporting are fulfilled, the investigator should not wait to receive additional information to fully document the event.

In addition, the investigator must:

- Report all SAEs to the relevant Institutional Review Board (IRB) / Independent Ethics Committee (IEC) within the timeframe specified by the IRB / IEC.
- Enter follow-up information in the eCRF until the SAE has resolved, or, in the case of permanent impairment, until stabilized.
- Ensure that the causality assessment for any SAE is entered in the eCRF.

In cases of death, the investigator should supply CSLB and the IEC / IRB (as applicable) with any additional information as it becomes available (eg, autopsy reports and detailed medical reports).

9.6.3 Medical Device Incidents

The investigator must promptly report all incidents occurring with any medical device provided for use in the study in order for CSLB to fulfill the legal responsibility to notify appropriate regulatory authorities and other entities about certain safety information relating to medical devices being used in clinical studies

Any event that meets the definition of a medical device incident must be documented in the appropriate page of the eCRF **immediately (within 24 hours of the investigator becoming aware of the event)**. Medical device incidents that meet the definition of an AE or SAE must also be reported as described in [Section 9.6.1](#) (AEs) and [Section 9.6.2](#) (SAEs).

9.6.4 Adverse Events of Special Interest Incidents

Adverse events of special interest, whether or not causally related to IgPro20 or IgPro10, must be reported and entered into the eCRF **immediately (within 24 hours of the event) to**

CSLB.

Any AESIs that occurs after the EOS Visit that is considered to be causally related to IgPro20 or IgPro10 must be reported **immediately (ie, within 24 hours of the investigator becoming aware of the event) to CSLB.**

9.6.5 Overdose

Any overdose that occurs in association with an adverse sign or symptom must be entered into the eCRF as an AE; if the AE meets any seriousness criteria, the event must be reported as an SAE (see [Section 9.6.2](#)).

Details (ie, volume, location of infusions, infusion rate) of administration of IgPro20 or IgPro10 (defined in [Section 5.1.3.2](#)) must be recorded in the study treatment administration eCRF. Details of overdose of any concomitant therapy must be recorded in the Concomitant Medication eCRF.

9.6.6 Pregnancy and Breastfeeding

A female subject who becomes pregnant while participating in the study, or up to and including 30 days after the last dose of IgPro20 or IgPro10, must notify the investigator immediately.

If a female subject becomes pregnant, she must discontinue treatment with IgPro20 or IgPro10, but may continue other study procedures at the discretion of the investigator. If the female subject is in the active treatment period of the study, her participation will be discontinued and the procedure for discontinuation of a subject will be followed, as described in [Section 4.3](#)).

CSLB must be notified within 5 days of the investigator becoming aware of the pregnancy.

Whenever possible, a pregnancy in a subject exposed to IgPro20 or IgPro10 should be followed to term so as to assess any potential occurrence of congenital anomalies or birth defects. Any follow-up information, including premature termination and the status of the mother and child after delivery, should be reported by the investigator to CSLB using a Pregnancy Reporting / Outcome Form.

9.7 IRB / IEC Reporting Requirements

The time frame within which an IRB / IEC must be notified of deaths and IP-related unexpected SAEs is stipulated by each IRB / IEC. It is the investigator's responsibility to

comply with the requirements for IRB / IEC notification. CSLB will provide investigators with all details of all SAEs reported to regulatory authorities.

10 Statistics

10.1 Sample Size Estimation

The sample size is mainly based on feasibility, not driven by power calculations for statistical hypothesis testing. However, based on the 9 IgPro20 studies completed by CSLB (8 studies on PID and 1 study in CIDP), the rate of ISRs per IgPro20 infusion is expected to be approximately 0.1, with 0.5 likely to be the maximum. With the target sample size of 20 subjects (10 patients per sequence) and each subject receiving 28 IgPro20 SC infusions, there are a total of 560 planned IgPro20 infusions overall for the entire study. If the rate of ISRs per infusion is 0.1, the study will have 80% chance to have a 95% CI with half width ≤ 0.0261 using Wilson score method; if the rate is 0.5, the half width of the 95% CI will be ≤ 0.0414 .

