IgPro20 (Hizentra[®], 20% normal human immunoglobulin) will be administered twice weekly during Treatment Period 1 (Sequence A) and Treatment Period 2 (Sequence B) by SC infusion at a total dose of 0.5g/kg/week for 16 weeks.

IgPro10 (Privigen[®], 10% normal human immunoglobulin) will be administered over 2 to 5 consecutive days every 4 weeks during Treatment Period 1 (Sequence B) and Treatment Period 2 (Sequence A) via IV infusion at a total dose of 2 g/kg/4 weeks for 16 weeks.

Comparator Product, Dose, Dosing Regimen and Administration

Not applicable.

Efficacy Assessments

CCI [Redacted]

Safety Assessments

Safety and tolerability as assessed by AEs, physical examination, vital signs, ECGs, pregnancy tests, PFTs, clinical laboratory tests, hemolysis, TEE, and renal function safety assessments, and patient diary completion and review.

Pharmacokinetics

The PK parameters $AUC_{0-\tau}$, $AUC_{0-\text{last}}$, C_{max} , and C_{trough} will be assessed in order to determine the relative bioavailability of IgPro20.

Other Assessments

CCI [Redacted]
 CCI [Redacted]
 CCI [Redacted]
 CCI [Redacted]

Statistical Analyses

The sample size is mainly based on feasibility, not driven by power calculations for statistical hypothesis testing. With the target sample size of 20 subjects (10 patients per sequence) and each subject receiving 28 IgPro20 SC infusions, there are a total of 560 planned IgPro20 infusions overall for the entire study. If the rate of ISRs per infusion is 0.1, the study will have 80% chance to have a 95% confidence interval with half width ≤ 0.0261 using Wilson score method; if the rate is 0.5, the half width of the 95% confidence interval will be ≤ 0.0414 .

Schedule of Assessments: Sequence A, Treatment Period 1 (IgPro20)

Visit ^{A,B}	Screening	Week 1		Week 3		Week 5		Week 7		Week 9		Week 11		Week 13		Weeks 2, 4, 6, 8, 10, 12		Week 14		Week 15	UNSC ^C	
		P	A	P	A	P	A	P	A	P	A	P	A	P	A	P	A	P	A			
Informed consent	X																					
Inclusion / exclusion criteria	X	X																				
Assess and record demographics	X																					
Assess and record medical history	X																					
Randomization ^D		X																				
Physical examination ^E	X	X		X		X		X		X		X		X								
Height	X																					
CCI		X																				
CCI		X																				
CCI		X																				
ECG	X	X																				
PFTs (CCI) ^F	X	X																				
Vital signs	X	X	X	X	X	X	X	X	X	X	X	X	X	X	X	X	X	X	X	X		

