2.1.2 Primary Endpoints

The primary endpoint of the study is the safety of IgPro20 based on:

Safety Endpoints	Summary Measure
AEs, including any AEs, treatment-emergent adverse events (TEAEs), serious adverse events (SAEs), and adverse events of special interest (AESIs)	
AEs measured by treatment, treatment sequence, combination of treatment, and treatment period (Period 1, Week 16; Period 2, Week 32; combination of treatment, Week 32):
 
 Number and percentage of subjects with AEs, TEAEs, SAEs, and AESIs (total, severity, causality, and outcome) Number and percentage of subjects with AEs categorized as ISRs (total, severity, causality and outcome) Rate of ISRs per subject and per infusion Onset and duration of ISRs
Change in other clinical tests	
Changes from baseline as measured by treatment, treatment sequence, combination of treatment and treatment period:
 
 Vital signs Body weight Clinical laboratory tests Electrocardiogram (ECG) Pulmonary function tests (PFTs)

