10.3.2 Analyses of Primary Endpoints

10.3.2.1 Safety of IgPro20

Safety data collected while subjects are treated with IgPro20 will be summarized by treatment sequence. All AEs will be coded by the Medical Dictionary for Regulatory Activities in System Organ Class and Preferred Term. Treatment-emergent adverse events, defined as AEs reported at or after the start of the first infusion in the study, will be summarized in number and percentages by treatment sequence. Summaries of TEAEs by

severity, causal relationship, seriousness, and leading to interruption and / or withdrawal will be provided.

Infusion site reactions will also be summarized separately following the analyses for all TEAEs. Additional summary statistics including 95% CIs will be presented for rate of ISRs per subject and per infusion. Descriptive statistics of time to onset and duration of ISRs will be presented. Detailed information about ISRs related to infusion sites will be provided.

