4.5 Determination of the Sample Size

The sample size for this study is not determined as based on hypothesis testing considerations. The sample size is mainly based on feasibility, not driven by power calculations for statistical hypothesis testing. However, based on the 9 IgPro20 studies completed by CSLB (8 studies on PID and 1 study in CIDP), the rate of ISRs per IgPro20 infusion is expected to be approximately 0.1, with 0.5 likely to be the maximum. With the target sample size of 20 subjects (10 subjects per Treatment Sequence) and each subject receiving 28 IgPro20 SC infusions, there are a total of 560 planned IgPro20 infusions overall

for the entire study. If the rate of ISRs per infusion is 0.1, the study will have 80% chance to have a 95% CI with half width ≤ 0.0261 using Wilson score method; if the rate is 0.5, the half width of the 95% CI will be ≤ 0.0414 .

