4.7 Interim Sample Size Re-estimation

Sample size re-estimation is not planned for this study.

5 Changes in the Conduct of Planned Analyses

The primary endpoint (CSP 2.1.2) requests to summarize AEs, TEAEs, AESIs, and SAEs in total and by severity and causality. In deviation to this, the summary of AEs will be restricted to TEAEs only.

In section CSP 2.2.2 “Secondary Endpoints” C_{trough} is defined as “minimum plasma drug concentration”. This is corrected to “trough plasma drug concentration”.

In section CSP 10.3.2.1 “Safety of IgPro20” 95% confidence intervals (CI) are requested for the rate of ISR per subject and per infusion. The CIs for the rate of ISR per infusion will not be calculated as the infusions are not statistically independent.

The Full Analysis Set (section CSP 10.2.1) is renamed to ITT Analysis Set, and the description was reworded for clarity. The definition of the set is not changed.

Section 10.4.2 of the CSP (Interim Analysis) states:

"An interim analysis is planned after all subjects randomized to Sequence A have finished IgPro20 treatment (Treatment Period 1). This interim analysis is planned for safety review and reporting."

The timing and purpose of the Interim Analysis has changed (see Section 4.6 of this SAP).

CSP section 10.3.3.1 requires "... subject as a random effect ..." in the model to assess relative bioavailability. This effect will not be applied.

6 Study Analysis Sets

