 - Causally related TEAEs by SOC and PT
 - Causally related TEAEs by SOC, PT, and maximum severity (without number of events)
 - Temporally associated TEAEs by SOC, PT and maximum severity (without number of events)
 - Temporally associated TEAEs and/or causally related TEAEs by SOC, PT and maximum severity (without number of events)
 - Serious TEAEs by SOC and PT
 - Serious, causally related TEAEs by SOC and PT
 - TEAEs leading to permanent discontinuation of IP by SOC and PT
 - Treatment-emergent AESIs by Category, SOC and PT
 - Treatment-emergent AESIs by Category and PT
 - Treatment-emergent AESIs by Category, PT and maximum grade (without number of events)
 - Treatment-emergent AESIs Grade 3 and above by Category and PT
 - Serious treatment-emergent AESIs by Category and PT

-
- Related treatment-emergent AESIs by Category and PT
 - All AE summaries presented by SOC and preferred term will include a virtual SOC “Infusion Site Reactions”, i.e., all AEs reported within the MedDRA High level terms “Administration site reactions NEC”, “Infusion site reactions” or “Injection site reactions”. AEs will be presented in the virtual SOC and the regular SOC.
 - All AE summaries presented by SOC and preferred term will include a virtual SOC “Thromboembolic Events” comprising all AEs reported within the MedDRA SMQs in [Section 11.3](#). AEs will be presented in the virtual SOC and the regular SOC.

Additional summary statistics for ISR will be presented for IgPro20 Treatment Periods only (see [Table 2](#)):

- Number and percent of subjects with ISR, incl. 95% Wilson score CI
- Number and percent of subjects with ISR per week, incl. 95% Wilson score CI
An ISR will be counted for the week of the most recent infusion before the onset of the ISR.
- ISR rate per Infusion
- ISR rate per Infusion per week
- Duration of ISR
- Time to onset of ISR since start of corresponding Treatment Period
- Time to onset of ISR since start of last infusion prior to onset of AE

$$\text{ISR rate per infusion} = \frac{\text{total number of ISRs across all subjects while on IgPro20}}{\text{total number of IgPro20 Infusions across all subjects}}$$

Temporally associated TEAEs are defined as AEs with an onset between the start of the infusion and up to 72 h after the end of infusion. In case time of onset of AE is missing, the AE is considered temporally related, if the onset of the AE is between the day of the start of infusion and the day of the end of infusion + 3 days (inclusive).

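### The per-infusion ISR rate loses its confidence interval in the SAP with no subject-clustered replacement, while the quoted planned precision still assumes 560 independent yes/no infusions

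*Protocol*

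**What the plan says.** Protocol 2.1.2 lists "Rate of ISRs per subject and per infusion" among the primary-endpoint measures. Protocol 10.3.2.1 commits to intervals for both: "Additional summary statistics including 95% CIs will be presented for rate of ISRs per subject and per infusion".

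Protocol 10.1 takes 20 subjects with 28 IgPro20 infusions each. It states that "the study will have 80% chance to have a 95% CI with half width" ≤ 0.0261 by the Wilson score method if the rate is 0.1, and ≤ 0.0414 if the rate is 0.5. The synopsis says the same ("the study will have 80% chance to have a 95% confidence interval with half width"). So does SAP 4.5, on the basis that "there are a total of 560 planned IgPro20 infusions overall".

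SAP Section 5 (Changes in the Conduct of Planned Analyses) then says: "The CIs for the rate of ISR per infusion will not be calculated as the infusions are not statistically independent".

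SAP 11.2 still reports the ISR rate per infusion, overall and per week, but without an interval. The numerator is the "total number of ISRs across all subjects while on IgPro20" and the denominator is all IgPro20 infusions. The ISR intervals that remain are for proportions of subjects: one for the whole treatment period, and one by week ("Number and percent of subjects with ISR per week, incl. 95% Wilson score CI").

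**The concern.** The SAP contradicts itself. Section 5 rejects independence of infusions, yet Section 4.5 keeps precision figures that depend on it. Lack of independence is a good reason to discard an infusion-level Wilson interval. It calls for a variance estimator that respects the subject; it does not justify reporting the rate with no interval.

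This rate is the only quantity in the plan with a stated planned precision. As written, it would be reported with no measure of uncertainty, in a study that tests no hypotheses and so conveys uncertainty through intervals. The subject-level Wilson intervals do not fill the gap: a subject with one ISR and a subject with twenty count the same. A reader of SAP 4.5 would also expect a precision that holds only without within-subject correlation and without repeat ISRs at one infusion.

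**Working it through.** **Inputs from the documents.** 20 subjects × 28 infusions = 560; rate 0.1 expected and 0.5 as likely maximum; 95% Wilson score interval (Protocol 10.1, SAP 4.5). Up to 4 simultaneous infusion sites (Protocol 5.1.3), so one infusion can produce more than one ISR. No intraclass correlation (ICC) or between-subject coefficient of variation (CV) is given; the values used below are assumptions.

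**Step 1: reproduce the stated figures.** The Wilson half width is

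h = z·√[p(1−p)/n + z²/(4n²)] / (1 + z²/n), with z = 1.96 and n = 560.

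- At p = 0.1, h = 0.0249. With the number of ISRs binomial(560, 0.1), P(h ≤ 0.0261) = 0.821. The smallest bound reached with at least 80% chance is 0.0260, at 62 ISRs.
- At p = 0.5, h = 0.0413, which is the Wilson maximum. The Wald value is 1.96·√(0.25/560) = 0.0414.

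The figures reproduce, but only under a binomial model: independent infusions, each with zero or one ISR. The documents do not write these two conditions out; they follow from Wilson with n = 560.

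**Step 2: yes/no infusions with within-subject correlation.** Effective n = 560 / (1 + 27·ICC), put into the same formula. The last two columns come from beta-binomial simulation (20 × 28, 100,000 runs) at rate 0.1.

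| ICC (assumed) | Effective n | h, rate 0.1 | h, rate 0.5 | 80%-assurance h, rate 0.1 | P(h ≤ 0.0261), rate 0.1 |
|---|---|---|---|---|---|
| 0 | 560 | 0.0249 | 0.0413 | 0.0260 | 82% |
| 0.01 | 441 | 0.0281 | 0.0465 | 0.030 | about 15% |
| 0.05 | 238 | 0.0383 | 0.0630 | 0.041 | about 0% |
| 0.1 | 151 | 0.0482 | 0.0787 | 0.052 | about 0% |
| 0.3 | 62 | 0.0764 | 0.1212 | 0.085 | about 0% |

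The fifth column is the one comparable with the stated 0.0261. An interval that ignores clustering would also under-cover: at rate 0.1, simulated coverage is 79% at ICC 0.05 and 68% at ICC 0.1. Dropping it was right.

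**Step 3: ISR counts, the measure SAP 11.2 defines.** Independent Poisson counts give 1.96·√(0.1/560) = 0.0262 and 1.96·√(0.5/560) = 0.0586. The matching expected binomial values are 0.0249 and 0.0413. So at rate 0.5 the stated 0.0414 is missed even without clustering. With between-subject variation and a subject-level bootstrap-t interval:

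| CV (assumed) | Median h, rate 0.1 | 80%-assurance h, rate 0.1 | Median h, rate 0.5 | 80%-assurance h, rate 0.5 |
|---|---|---|---|---|
| 0.5 | 0.036 | 0.044 | 0.13 | 0.16 |
| 1 | 0.055 | 0.077 | 0.25 | 0.34 |
| 1.5 | 0.083 | 0.136 | 0.39 | 0.60 |

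**Step 4: does a clustered interval work with about 20 subjects?** The bootstrap-t was simulated at rates 0.03, 0.1 and 0.5, with equal clusters, ICC 0.01 to 0.3 and CV 0.5 to 1.5. Coverage was 93.8 to 97.0%. With unequal clusters (assumed 23 treated, 25% stopping early; rates 0.1 and 0.5) it was 92.8 to 96.3%. A log-scale ratio interval with t on n−1 degrees of freedom covered 91.6 to 95.7% and 91.1 to 95.9% respectively.

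The bootstrap-t needs at least 4 reacting subjects. With 3 of 20, (17/20)^20 = 3.9% of resamples contain no reactor, more than the 2.5% tail, and the upper limit is not finite. With 4 of 20 the share is (16/20)^20 = 1.2%. The bootstrap-t coverage figures exclude trials below that threshold: at most 0.1% of trials at rates 0.1 and 0.5, but 52% at rate 0.03 with ICC 0.3.

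**The case against.** SAP Section 5 discloses the change openly and gives a correct reason; withholding an invalid interval is better than printing one. The sample size is mainly feasibility-based, nothing is tested, and no decision hangs on the interval. SAP 11.2 keeps subject-level Wilson intervals, overall and by week, and every ISR is listed, so with about 20 subjects a reader can see clustering directly. All of this stands. It limits the consequence but supplies no interval for the event rate and leaves SAP 4.5 at odds with Section 5.

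The size of the effect rests on assumed ICC and CV values, and the results span a wide range. That is so: they show direction and plausible scale, not a forecast. The tables also use different interval types, and the bootstrap-t interval is asymmetric, so a half width summarises it only roughly. Still, an ICC of 0.01 is enough to defeat the 80% statement.

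About 26 subjects will be enrolled and the safety set includes everyone treated, so intervals may be somewhat narrower than for 20. If all 26 received every infusion, the factor would be about √(20/26) = 0.88, which does not restore the stated figures at ICC 0.05 or above.

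Finally, offering two interval methods is not pre-specification. That is fair: the SAP must name one.

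**Conclusion.** The concern holds. A promised interval for a primary-endpoint measure is withdrawn without replacement, and the precision still quoted depends on independence that the SAP itself denies and on at most one ISR per infusion, which its numerator does not respect. The arithmetic in Protocol 10.1 is correct under its own model; the model does not fit.

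Under the assumed ICCs of 0.01 to 0.3, the expected half width is about 1.1 to 3 times the independent value (0.0281/0.0249 to 0.0764/0.0249 at rate 0.1; 0.0465/0.0413 to 0.1212/0.0413 at rate 0.5). For ISR counts with CV 0.5 to 1.5, median half widths are about 0.04 to 0.08 at rate 0.1 and 0.13 to 0.39 at rate 0.5.

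This should be fixed before database lock. It does not threaten the sample size or any study decision.

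**What to change.** 1. **SAP 4.5** (and Protocol 10.1 and the synopsis at the next amendment, if there is one). Add: *The half widths 0.0261 and 0.0414 assume independent infusions with at most one ISR each. Within-subject correlation is not known; under assumed values the CI is wider. Yes/no infusions, ICC 0.01 to 0.3: expected Wilson half width at effective n about 0.03 to 0.08 (rate 0.1) and 0.05 to 0.12 (rate 0.5). ISR counts, between-subject CV 0.5 to 1.5: median subject-level bootstrap-t half width about 0.04 to 0.08 (rate 0.1) and 0.13 to 0.39 (rate 0.5).*

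2. **SAP 11.2.** Report total ISRs divided by total IgPro20 infusions with one pre-specified 95% CI that treats the subject as the cluster. Choose one of:
   - Subject-level bootstrap-t: resample subjects with their ISR and infusion counts together, use the linearized ratio standard error and a fixed seed, and truncate the lower limit at 0. If fewer than 4 subjects have an ISR, or a limit is not finite, report the rate with the subject-level Wilson CI only.
   - Log-scale ratio interval with t on n−1 degrees of freedom. It is closed-form and simpler, with slightly lower coverage. It is undefined with no ISRs, in which case the same Wilson fallback should apply.

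3. **SAP Section 5.** Replace the statement that the interval is not calculated with: *the infusion-level Wilson CI is replaced by a subject-clustered CI.*

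Keep n = 20 and the existing subject-level Wilson intervals.

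**Cost.** SAP wording and one extra analysis of data already collected; no new patients, visits or procedures. The protocol sentence does not affect conduct and appears to fit the administrative category in Protocol 13.3. The downside is a less favourable stated precision.
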